**Table 3: Cholesterol Elevations Dose Modifications/Interruptions**

Toxicity	Dose Modification/Interruption	Toxicity Management
Grade 3	Hold protocol therapy until values return to $\leq$ Grade 2 ( $\leq 400$ mg/dL) fasting cholesterol. Then resume rucaparib at same dose.	Consider the use of concomitant treatment with a HMG-CoA reductase inhibitor (commonly known as statin). However, caution should be noted for the use of certain statin drugs. See Section 3.1c.3 .

#### 8.5 Adverse Event Reporting

Toxicities (including suspected reactions) that meet the expedited reporting criteria as outlined in [Section 16.0](#) of [S1900A](#) must be reported to the Operations Office, Study Chair and NCI via CTEP-AERS, and to the IRB per local IRB requirements.

## 9.0 STUDY CALENDAR

### 9.1 Rucaparib

REQUIRED STUDIES	PRE-STUDY (w/in 28 days prior to registration, unless otherwise noted)	Cycle Length = 21 days (+/- 3 days)					At Off Tx	Off Tx FU Prior to Prog	Off Tx FU After Prog 
		Cycle 1	Cycle 2	Cycle 3	Cycle 4	Subsequent Cycles 			
PHYSICAL									
History & Physical Exam	X	X	X	X	X	X	X	X 	
Weight & Performance Status	X	X	X	X	X	X	X	X 	
Intake Calendar 		X	X	X	X	X			
Toxicity Notation		X	X	X	X	X	X	X 	X 
Smoking Status Assessment	X						X		
LABORATORY									
	If labs obtained w/in 14 days prior to tx, tests need not be repeated on C1D1.		Up to 48 hours prior to Day 1 tx						
CBC/Diff/Platelets/Hgb	X	X	X	X	X	X	X	X 	X 
Serum Bilirubin	X	X	X	X	X	X	X	X 	X 
ALT or AST 	X	X	X	X	X	X	X	X 	X 
Alkaline Phosphatase	X	X	X	X	X	X	X	X 	X 
Cholesterol (fasting) 	X (per Sec. 5.1a4)	X	X	X	X	X	X	X 	X 

REQUIRED STUDIES	PRE-STUDY (w/in 28 days prior to registration, unless otherwise noted)	Cycle Length = 21 days (+/- 3 days)					At Off Tx	Off Tx FU Prior to Prog	Off Tx FU After Prog 
		Cycle 1	Cycle 2	Cycle 3	Cycle 4	Subsequent Cycles 			
Serum Creatinine/Calc CrCl	X	X	X	X	X	X	X	X 	X 
Serum Pregnancy Test		X  (w/in 7 days prior to C1D1)							
X-RAYS & SCANS									
CT or MRI for Disease Assessment 	X			X (every 6 wks, ± 7 days)		X (every 6 wks, ± 7 days)		X  (every 12 wks, ± 7 days)	
Brain CT/MRI 	X				X (every 12 wks, ± 7 days)	X (every 12 wks, ± 7 days)		X (every 12 wks, ± 7 days)	
SPECIMEN SUBMISSION									
ctDNA Whole Blood		X 							
Buffy Coat /Plasma for Banking 	X (pre-tx)		X	X	X				X (first progression)
TREATMENT (21 day cycle)									
Rucaparib 		X	X	X	X	X			

NOTE: Forms are found on the protocol abstract page on the CTSU website ([www.ctsu.org](http://www.ctsu.org)). Forms submission guidelines are found in [Section 14.0](#).

NOTE: Unless indicated otherwise in the protocol, scheduled procedures and assessments (treatment administration, toxicity assessment for continuous treatment, disease assessment, specimen collection and follow-up activities) must follow the established SWOG guidelines on the allowed protocol visits/treatment window as outlined in <https://www.swog.org/sites/default/files/docs/2019-07/BestPracticesupdate.pdf>. SWOG Best Practices allows for a ± 3 day window for 21-day cycles.

**Footnotes for Calendar 9.1 (Rucaparib):**

- 1 CT or MRI (the same method used at pre-study to meet the eligibility criteria in [Section 5.2 S1900A](#)) must be repeated every 6 weeks ( $\pm$  7 day window) for the first year, regardless of treatment delays, then every 12 weeks ( $\pm$  7 day window) until disease progression and discontinuation of protocol treatment. The 6 weeks should start from Cycle 1 Day 1. Submit scans as outlined in [Section 14.0](#) and [Section 15.0 S1900A](#).
- 2 Brain CT or MRI is required per [Section 5.2](#). If patient has brain metastases at baseline, brain scans must use the same modality as baseline and be repeated every 12 weeks ( $\pm$  7 days) regardless of treatment delays, while on treatment. If patient has brain metastases at baseline, continue brain CT or MRI scans (same modality as baseline) after off protocol treatment prior to progression, as clinically indicated. For alignment with the protocol and good clinical practice, recommended frequency of brain scans after off protocol treatment (and prior to progression) is at least every 12 weeks, unless more frequent scans are clinically appropriate.
- 3 If ALT/AST elevation of  $\geq$  Grade 3, monitor liver function tests weekly until resolution to  $\leq$  Grade 2. See [Section 8.3 Table 2](#).
- 4 During continued treatment, items marked under physical and laboratory should be performed prior to every subsequent cycle, unless otherwise noted. Disease assessments and image submission are to take place every 6 weeks ( $\pm$  7 days) regardless of treatment delays. Treatment and evaluation will continue until any one of the criteria in [Section 7.5 S1900A](#) is met.
- 5 After off protocol treatment prior to progression, patients should be followed by repeating indicated studies every 12 weeks or more often as clinically indicated until progression. Disease assessments should continue every 12 weeks until progression.
- 6 After off protocol treatment after progression, follow-up will occur (with lab tests and scans performed at the discretion of the treating physician) every 6 months for 2 years then at end of 3 years from date of sub-study registration. Note: Patients who enroll on a new sub-study following progression must continue follow-up on this sub-study, in addition to follow-up on the new sub-study.
- 7 This footnote has been removed.
- 8 Assessments should continue until resolution of all acute adverse events.
- 9 The CRA will review the Intake Calendar at the end of each cycle and confirm patient adherence (See Intake Calendar for site and patient instructions in [Section 18.6](#))
- 10 ctDNA must be collected prior to treatment initiation per [Section 15.3](#). Note: Kits must be ordered and will take up to 3 days to arrive.
- 11 Women of child bearing potential must have a negative serum pregnancy test within 7 days prior to Cycle 1 Day 1.
- 12 Pre-Study fasting cholesterol to be performed as clinically indicated per Section 5.1a4. It is acceptable to perform a non-fasting test for subsequent timepoints; however, if the participant experiences a  $\geq$  Grade 3 hypercholesterolemia, a follow-up fasting cholesterol check must be performed. If  $\geq$  Grade 3 hypercholesterolemia is confirmed, proceed to managing the toxicity as outlined in [Section 8.3 Table 3](#).
- 13 See [Section 15.2](#) for details.

## 10.0 CRITERIA FOR EVALUATION AND ENDPOINT ANALYSIS

### 10.1 Measurability of Lesions (28)

a. **Measurable disease:** Measurable disease is defined differently for lymph nodes compared with other disease and will be addressed in a separate section below.

1. Lesions that can be accurately measured in at least one dimension (longest diameter to be recorded) as  $\geq 2.0$  cm by chest x-ray, by  $\geq 1.0$  cm with CT or MRI scans, or  $\geq 1.0$  cm with calipers by clinical exam. All tumor measurements must be recorded in decimal fractions of centimeters (or millimeters).

The defined measurability of lesions on CT scan is based on the assumption that CT slice thickness is 0.5 cm or less. It is strongly recommended that CT slice of 0.5 cm be used. If CT scans have slice thickness greater than 0.5 cm, the minimum size for a measurable lesion should be twice the slice thickness.

2. **Malignant lymph nodes** are to be considered pathologically enlarged and measurable if it measures  $\geq 1.5$  cm in **SHORT AXIS** (greatest diameter perpendicular to the long axis of the lymph node) when assessed by scan (CT scan slice recommended being no greater than 0.5 cm).

b. **Non-measurable disease:** All other lesions (or sites of disease), including small lesions (longest diameter  $< 1.0$  cm or pathologic lymph nodes with  $\geq 1.0$  cm to  $< 1.5$  cm short axis), are considered non-measurable disease. Bone lesions, leptomeningeal disease, ascites, pleural/pericardial effusions, lymphangitis cutis/pulmonitis, inflammatory breast disease, and abdominal masses (not followed by CT or MRI), are considered as non-measurable as are previously radiated lesions that have not progressed.

#### c. Notes on measurability

1. For CT and MRIs, the same type of scanner should be used and the image acquisition protocol should be followed as closely as possible to prior scans. It is no longer necessary to distinguish between spiral and conventional CT.
2. Body scans should be performed with breath-hold scanning techniques, if possible.
3. PET-CT: At present, the low dose or attenuation correction CT portion of a PET-CT is not always of optimal diagnostic CT quality for use with RECIST measurements. However, if the site can document that the CT performed as part of a PET-CT is of identical diagnostic quality to a diagnostic CT, then the CT portion of the PET-CT can be used for RECIST measurements and can be used interchangeably with stand-alone CT. *The slice thickness of 0.5 cm or less is highly recommended.* If CT scans have slice thickness  $> 0.5$  cm, the minimum size for a measurable lesion should be twice the slice thickness.
4. Ultrasound: Ultrasound is not useful in assessment of lesion size and should not be used as a method of measurement.
5. Cystic lesions that meet the criteria for radiographically defined simple cysts should not be considered as malignant lesions (neither measurable nor non-measurable) since they are, by definition simple cysts.

6. If a target lesion becomes very small some radiologists indicate that it is too small to measure. If the lesion is actually still present, a default measurement of 0.5 cm should be applied. If the radiologist believes the lesion has gone, a default measurement of 0.0 cm should be recorded.

#### 10.2 Objective Status at Each Disease Evaluation

Objective Status is to be recorded at each evaluation. All measurable lesions up to a maximum of 2 lesions per organ, 5 lesions in total, representative of all involved organs, should be identified as target lesions at baseline. All other lesions (or sites of disease) including any measurable lesions over and above the 5 target lesions should be identified as non-target lesions. Measurements must be provided for target measurable lesions, while presence or absence must be noted for non-target measurable and non-measurable disease.

For studies that use disease progression as an endpoint, all potential sites of metastases should be evaluated at each time point rather than following only sites of disease identified at baseline. It is acceptable to image only the areas of the body most likely to be involved with metastatic disease for the tumor type (chest, abdomen, pelvis, and/or bone scan are typical), with the addition of any areas with suspected involvement based upon clinical symptoms. For study-specific imaging requirements, see the Study Calendar in [Section 9.0](#).

- a. **Complete Response (CR):** Complete disappearance of all target and non-target lesions (with the exception of lymph nodes mentioned below). No new lesions. No disease related symptoms. Any lymph nodes (whether target or non-target) must have reduction in short axis to < 1.0 cm. All disease must be assessed using the same technique as baseline.
- b. **Partial Response (PR):** Applies only to patients with at least one measurable lesion. Greater than or equal to 30% decrease under baseline of the sum of appropriate diameters of all target measurable lesions. No unequivocal progression of non-measurable disease. No new lesions. All target measurable lesions must be assessed using the same techniques as baseline.
- c. **Stable:** Does not qualify for CR, PR, Progression or Symptomatic Deterioration. All target measurable lesions must be assessed using the same techniques as baseline.
- d. **Progression:** One or more of the following must occur: 20% increase in the sum of appropriate diameters of target measurable lesions over smallest sum observed (over baseline if no decrease during therapy) using the same techniques as baseline, as well as an absolute increase of at least 0.5 cm. Unequivocal progression of non-measurable disease in the opinion of the treating physician (an explanation must be provided). Appearance of any new lesion/site. Death due to disease without prior documentation of progression and without symptomatic deterioration (see 10.2e).

**Notes on progression and new lesions:**

1. For equivocal findings of progression (e.g. very small and uncertain new lesions; cystic changes or necrosis in existing lesions), treatment may continue until the next scheduled assessment. If at the next scheduled assessment, progression is confirmed, the date of progression should be the earlier date when progression was suspected.
2. FDG-PET imaging can complement regular scans in identifying new lesions according to the following algorithm.
  - Negative FDG-PET at baseline, with a positive FDG-PET at follow-up is a sign of progression based on a new lesion.
  - No FDG-PET at baseline and a positive FDG-PET at follow-up corresponding to a potential new site of disease must have a confirmation by anatomical assessment (e.g. CT, MRI, x-ray) as new site of disease to be considered progressive disease. In such a case, the date of progressive disease will be the date of the initial abnormal FDG-PET.
3. A previous abnormal target lymph node that became normal and subsequently enlarged in size meeting the criteria for a pathologic and measurable lymph node (a short axis of  $\geq 1.5$  cm) should be added to the sum of diameters to determine if criteria for progression are met based on target lesions.
4. A previously abnormal non-target lymph node that became normal and subsequently recurred must meet the criteria for progression based on non-target lesions to be considered progression.
5. A normal lymph node at baseline ( $<1.0$  cm) that subsequently becomes pathologic is considered a new lesion and should be considered progression.
6. If a single pathologic lymph node is driving the progression event, continuation of treatment/follow-up and confirmation by a subsequent exam should be contemplated. If it becomes clear that the new lymph node has not resolved, or has increased in size, the date of progression would be the date the new lymph node was first documented.

e. **Symptomatic deterioration:** Global deterioration of health status requiring discontinuation of treatment without objective evidence of progression. Efforts should be made to obtain objective evidence of progression after discontinuation.

f. **Assessment inadequate, objective status unknown:** Progression or symptomatic deterioration has not been documented, and one or more target measurable lesions have not been assessed or inconsistent assessment methods were used.

**Objective status notes:**

1. Non-measurable and non-target measurable disease do not affect Objective Status in determination of CR (must be absent—a patient who otherwise has a CR, but who has non-measurable or non-target measurable disease present or not assessed, will be classified as having a PR). However, non-measurable and non-target lesions are included in

determination of progression (if new sites of disease develop or if unequivocal progression occurs in the opinion of the treating physician).

2. An objective status of PR or stable cannot follow one of CR. Stable can follow PR only in the rare case that tumor increases too little to qualify as progression, but enough that a previously documented 30% decrease no longer holds.
3. In cases for which initial flare reaction is possible (hypercalcemia, increased bone pain, erythema of skin lesions), objective status is not progression unless either symptoms persist beyond 4 weeks or there is additional evidence of progression.
4. Lesions that appear to increase in size due to presence of necrotic tissue will not be considered to have progressed.
5. For bone disease documented on bone scan only, increased uptake does not constitute unequivocal progression. However, increase in the soft tissue component of a lesion as measured by CT or MRI would constitute progression.
6. Appearance of new pleural effusions does not constitute unequivocal progression unless cytologically proven of neoplastic origin, since some effusions are a toxicity related to therapy or other medical conditions. Increase in the size of an existing effusion does not constitute unequivocal progression, since the fluid status of the patient could alter the size of the effusion.
7. If CR determination depends on a lesion for which the status is unclear by the required tests, it is recommended the residual lesion be investigated with biopsy or fine needle aspirate.
8. Lymph nodes are considered one organ. Only two lymph nodes should be selected as target lesions. Other involved lymph nodes should be assessed and followed as non-target lesions.
9. "Paired" organs, i.e. lungs, kidneys and ovaries, are considered one organ.
10. Pleural-based lung lesions are considered part of the lung in determining target lesions (a maximum of two lung lesions should be selected), whereas pleural effusions/thickening can be reported as a separate site.

### 10.3 Best Response

This is calculated from the sequence of objective statuses.

- a. CR: Two or more objective statuses of CR a minimum of four weeks apart documented before progression or symptomatic deterioration.
- b. PR: Two or more objective statuses of PR or better a minimum of four weeks apart documented before progression or symptomatic deterioration, but not qualifying as CR.
- c. Unconfirmed CR: One objective status of CR documented before progression or symptomatic deterioration but not qualifying as CR or PR.
- d. Unconfirmed PR: One objective status of PR documented before progression or symptomatic deterioration but not qualifying as CR, PR or unconfirmed CR.
- e. Stable/no response: At least one objective status of stable/no response documented at least 6 weeks after registration and before progression or symptomatic deterioration, but not qualifying as anything else above.
- f. Increasing disease: Objective status of progression within 12 weeks of registration, not qualifying as anything else above.

- g. Symptomatic deterioration: Objective status of symptomatic deterioration within 12 weeks of registration, not qualifying as anything else above.
- h. Inadequate assessment, response unknown: Progression or symptomatic deterioration greater than 12 weeks after registration and no other response category applies.

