## 1.0 OBJECTIVES

### 1.1 Primary Objective

- a. To evaluate the overall response rate (ORR) (confirmed and unconfirmed, complete and partial) associated with rucaparib in patients with genomic LOH high and/or deleterious BRCA1/2 mutations within:
  - i. Cohort 1: Patients with squamous cell histology
  - ii. Cohort 2: Patients with non-squamous histology (adenocarcinoma, large cell, NSCLC NOS, or mixed histology with any non-squamous component)

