### 5.1 Sub-Study Specific Criteria

#### a. Sub-Study Specific Disease Related Criteria/ Laboratory Criteria

1. Patients must be assigned to **S1900A**. **S1900A** biomarker eligibility defined as LOH high and/or deleterious BRCA1/2 mutation is as follows using the FMI tissue- assay:

Biomarker-positive group	Alteration type	Eligible alteration
--------------------------	-----------------	---------------------

LOH	Loss of Heterozygosity (LOH)	Genomic LOH $\geq$ 21%
BRCA	Homologous Recombination Deficiency (HRD)	Deleterious mutations in BRCA1 or BRCA2

2. Patients must not have had prior treatment with any PARP inhibitor, including rucaparib, talazoparib, veliparib, olaparib, or niraparib. For information and a list of PARP inhibitors, please consult the [S1900A](#) – Poly Polymerase Inhibitors, Scott et al., 2015 JCO ref from the link on the [S1900A](#) protocol abstract page of the SWOG (<http://swog.org>) or CTSU (<https://www.ctsu.org>) websites.
3. Patients must be able to take oral medications.
4. Patients with known  $\geq$  Grade 3 hypercholesterolemia must be  $\leq$  Grade 2 ( $\leq 400$  mg/dL) within 28 days prior to sub-study registration. (Fasting cholesterol is required to be performed pre-registration only in those patients where clinically indicated.) Note: Use of medication to lower cholesterol is acceptable. Caution should be noted for the use of certain statin drugs. See Section [3.1c.3](#).

$\geq$  Grade 3 hypercholesterolemia ("cholesterol high") is defined by NCI CTCAE v5 as blood cholesterol measurement  $> 400$  mg/dL

b. **Sub-Study Specific Prior/Concurrent Therapy Criteria**

1. Patients must not be planning to receive any concurrent chemotherapy or small molecular or hormonal therapy within 21 days and biologics (e.g. bevacizumab, necitumumab or ramucirumab) or immunotherapy within 28 days prior to sub-study registration and while receiving treatment on this study. Concurrent use of hormones for non-cancer-related conditions (e.g., insulin for diabetes and hormone replacement therapy) is acceptable.

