**Disease Assessment During Off Protocol Treatment, Prior to Progression**

After off protocol treatment prior to progression, disease assessments must continue every 12 weeks ( $\pm$  7 day window) until progression.

If patient has brain metastases at baseline, continue brain CT or MRI scans (same modality as baseline) after off protocol treatment prior to progression, as clinically indicated. For alignment with the protocol and good clinical practice, recommended frequency of brain scans after off protocol treatment (and prior to progression) is at least every 12 weeks, unless more frequent scans are clinically appropriate.

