7.6 Criteria for Removal from Protocol Treatment

- a. Progression of disease or symptomatic deterioration (as defined in [Sections 10.2d](#) and [10.2e](#)). \*

\* Upon progression, the Request for New Sub-Study Assignment Form may be submitted under the patient's screening protocol ([LUNGMAP](#) or [S1400](#)) to receive a new sub-study assignment (see [Section 14.4i](#)).

- b. Unacceptable toxicity.
- c. Treatment delay for any reason > 28 days (or as noted in [Section 8.0](#)).
- d. The patients may withdraw from the protocol treatment at any time for any reason.

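### Best response has no cut at the start of other anticancer therapy, so a response to a later drug could count in the primary ORR attributed to rucaparib; the bias is upward and probably small

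*Combined protocol and SAP*

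**What the plan says.** The primary objective in Section 1.1 is "To evaluate the overall response rate (ORR) (confirmed and unconfirmed, complete and partial) associated with rucaparib", within each histology cohort.

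Section 10.3 defines best response: "This is calculated from the sequence of objective statuses". Each response category, confirmed or unconfirmed, must be documented before progression or symptomatic deterioration. For an unconfirmed PR the rule is "One objective status of PR documented before progression or symptomatic deterioration but not qualifying as CR, PR or unconfirmed CR". No category mentions the end of rucaparib or the start of another drug.

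Section 7.6 lists ways to leave rucaparib without progression: unacceptable toxicity, "Treatment delay for any reason > 28 days", and "The patients may withdraw from the protocol treatment at any time for any reason".

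Scanning then goes on. Section 7.1 states: "After off protocol treatment prior to progression, disease assessments must continue every 12 weeks", until progression. Footnote 5 of the Section 9.1 calendar agrees: "Disease assessments should continue every 12 weeks until progression". Section 14.4d collects a tumor assessment form for each of these off-treatment scans.

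Section 5.1b.1 restricts other anticancer therapy in a window before registration and "while receiving treatment on this study". It sets no limit afterwards. Section 11.2 adds no cut at new therapy, and neither do the definitions of IA-PFS and duration of response (Sections 10.6 and 10.8).

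**The concern.** Take a patient who stops rucaparib for toxicity with stable disease, starts another anticancer drug before progression, and shows a PR at the next 12-weekly scan. The form is collected, the status joins the sequence, and neither progression nor symptomatic deterioration has occurred. Under Section 10.3 this patient has an unconfirmed PR and counts toward the ORR attributed to rucaparib.

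The error runs one way. A later drug can add a counted response but cannot remove one already documented. There is no control arm in which the same thing would happen, and Section 12.1 triggers central review only if it is needed for FDA evaluation. The ORR rule is a fixed count, at least 10 of 40 per cohort, so even a fraction of an extra response shifts its error rate.

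The gap looks unintended. For late adverse events, Section 14.4f limits reporting to the time before non-protocol treatment. The same limit is not applied to response.

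**Working it through.** **Inputs from the plan (Sections 11.1 and 11.2).** Null ORR 15%, alternative 35%; 40 evaluable patients per cohort; interim at 20; stop for futility at 2 or fewer responses; success at 10 or more of 40. Stated exact type I error 6.6% and power 93%.

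**Step 1: reproduce the stated figures.** With X1 the responses in the first 20 patients and X2 those in the second 20,

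P(success | p) = sum over x = 3 to 20 of P(X1 = x) × P(X2 ≥ 10 − x), both Binomial(20, p).

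- p = 0.15: 0.0657, matching 6.6%
- p = 0.35: 0.9311, matching 93%

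The design arithmetic is sound.

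**Step 2: let later-drug responses in.** Two quantities are needed that the documents do not give, so both are assumptions:

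- f = share of rucaparib non-responders who start another drug before progression or symptomatic deterioration and are scanned on it, taken as 1% to 15%
- r = share of those who reach a PR or CR on it, taken as 10% to 20%

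At a true rucaparib ORR of 15%:

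- counted ORR = 0.15 + 0.85 × f × r
- expected extra responses per 40 = 40 × 0.85 × f × r

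Putting the counted ORR into the formula of Step 1 gives:

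| f | r | Counted ORR | Extra per 40 | Type I error |
|---|---|---|---|---|
| none | none | 15.0% | 0 | 6.6% |
| 1% | 10% | 15.1% | 0.03 | 6.8% |
| 2% | 10% | 15.2% | 0.07 | 7.0% |
| 5% | 10% | 15.4% | 0.17 | 7.7% |
| 5% | 20% | 15.9% | 0.34 | 8.9% |
| 10% | 15% | 16.3% | 0.51 | 10.2% |
| 10% | 20% | 16.7% | 0.68 | 11.6% |
| 15% | 20% | 17.6% | 1.02 | 14.8% |

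**Step 3: allow for timing.** Step 2 puts the extra responses into both stages. Off-treatment scans come only every 12 weeks, while the interim is paced around the second disease assessment, about 12 weeks in on the 6-weekly schedule. Later-drug responses among the first 20 patients would therefore tend to arrive after the interim. If they enter the final count only, the 7.7%, 10.2% and 14.8% become 7.6%, 9.9% and 14.0%.

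**Step 4: what one credited response does.** If one later-drug response is in the final count, 9 responses to rucaparib are enough. The chance of passing the interim and reaching at least 9 of 40 at p = 0.15 is 13.0%, about twice 6.6%. This is conditional on such a response occurring. It does not say how likely that is.

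**The case against.** The path is narrow, and every step must happen. The patient must not have responded on rucaparib, must stop without progression and without symptomatic deterioration, must start another drug before progression, must not progress by the next scan, and must then show a fall of at least 30% from the original baseline (Section 10.2b). Global decline that forces discontinuation is symptomatic deterioration under Section 10.2e and already closes the window. A new Lung-MAP sub-study is offered upon progression (Sections 7.6 and 14.4i), so responses there are already excluded. All of this stands and limits the size.

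The rates are assumed. Nothing in the documents shows whether f is nearer 1% or 15%, and at 1-2% with r = 10% the effect is negligible. This stands too. A reader might infer from the upper rows of the table that the false-positive rate is double the stated one. The documents do not support that, because those rows rest on assumed rates.

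A reader might also infer that development turns on a single response, 10 versus 9 of 40. That is true of the formal ORR rule only. Nine of 40 is 22.5%, and Section 11.2 says that with an ORR below 25% a median IA-PFS of at least 4.5 months may be considered sufficient to continue to Phase III.

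The LUNGMAP screening protocol is not among the documents and could hold a relevant rule. Section 10.3 reads as self-contained and does not refer to it for response, so this carries little weight.

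None of these points supplies the missing cut.

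**Conclusion.** The gap is real and lies in the primary endpoint. Followed as written, Section 10.3 credits rucaparib with a response to a later drug, and one unconfirmed PR is enough. The bias can only raise ORR.

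Its size cannot be taken from the documents and is probably small, because the path needs several uncommon steps in sequence. The range of 6.8% to 14.8% for type I error is illustrative, rests wholly on the assumed f and r, and models a true ORR of 15%. The stated 6.6% and 93% are correct for a response that is counted properly; the sample size and the decision rule are not at fault. Nor does the text suggest that early stopping in itself yields false responses: only a switch before both progression and symptomatic deterioration can. The clause is worth adding, but the gap does not undermine the design.

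**What to change.** In Section 10.3, state that:

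- only objective statuses recorded before the start of any non-protocol anticancer therapy count toward CR or PR, confirmed or unconfirmed;
- patients with no response by then stay in the denominator as non-responders.

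In Section 10.8, define the responders for duration of response in the same way, so that a later-drug response does not enter that analysis.

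Confirm that the Off Treatment Notice or the Advanced NSCLC Follow-Up Form records the start date of non-protocol anticancer therapy. Section 14.4 names both forms but does not show their contents, and the rule cannot be applied without that date.

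The cost is a short text change, one added date field if it is not already collected, and possibly a slightly lower ORR. It needs no new visits, no new scans and no change to the sample size. The stated 6.6% and 93% would then apply to response before any later drug.
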